9.1.3.1 Pregnancy or Breastfeeding

Pregnancy

Pregnancy itself is not regarded as an AE unless there is a suspicion that the medicinal product has interfered with a contraceptive method. If pregnancy occurs whilst using the medicinal product, the outcome of the pregnancy will then need to be collected. This applies irrespective of whether the pregnancy is considered to be related to interference by the medicinal product with a contraceptive method.

Details of all pregnancies in female participants and, if indicated, female partners of male participants will be collected from the signing of the ICF and until at least 5 months after EoS.

The investigator is to report to the Sponsor if they become aware of a pregnancy occurring in the partner of a participant participating in the study. If the female partner gives her consent, the pregnancy outcome should be followed up and reported.

Information regarding any pregnancies must be collected on the SS section of eCRF, including those with normal progress and throughout the Drug exposure for Pregnancy form (080479-FOR).

Abnormal pregnancy outcomes (e.g. spontaneous abortion, foetal death, stillbirth, congenital abnormalities, ectopic pregnancy) are considered SAEs. If there is an abnormal pregnancy outcome or an AE is reported in the foetus/neonate/child following exposure to a marketed Ipsen product, attempt to follow-up until one month after delivery.

The investigator must instruct all female participants to inform them immediately should they become pregnant whilst using the study medication.

Reports of pregnancy must be reported to Ipsen within 24 hours of the investigator's knowledge.

Breastfeeding

Any use of an IPSEN product during lactation/breastfeeding must be collected on the SS eCRF.

9.1.3.2 Overdose, Off-label Use, Misuse, Abuse, Occupational Exposure, and Medication Error

Overdose

Any dose higher than the maximum recommended dose in local label/SmPC, or in the protocol. For products which require gradual titration, any dose (initial or maintenance) which is higher than the recommended regime in the protocol, or labelling text will be assessed as 'overdose'. Overdoses should be reported as AEs in the AE eCRF page whether or not they were associated with a clinical event. All overdoses should be reported to Ipsen within 7 calendar days.

Off-label Use

PAGE 41/52

Off-label use relates to situations where the medicinal product is intentionally used for a medical purpose not in accordance with the terms of the marketing authorisation.

Off-label use should be reported as AEs in the AE eCRF page whether or not they were associated with a clinical event. All Off-label use should be reported to Ipsen within 7 calendar days.

Misuse

Misuse refers to situations where the medicinal product is intentionally and inappropriately used not in accordance with the terms of the marketing authorisation.

Misuse should be reported as AEs in the AE eCRF page whether or not they were associated with a clinical event. All misuse should be reported to Ipsen within 7 calendar days.

Abuse

Abuse corresponds to the persistent or sporadic, intentional excessive use of a medicinal product, which is accompanied by harmful physical or psychological effects.

Abuse should be reported as AEs in the AE eCRF page whether or not they were associated with a clinical event. All abuse should be reported to Ipsen within 7 calendar days.

Occupational exposure

Occupational exposure refers to the exposure to a medicinal product, as a result of one's professional or non-professional occupation. It does not include the exposure to one of the ingredients during the manufacturing process before the release as finished product.

Occupational exposure should be reported as AEs in the AE eCRF. All occupational exposure should be reported to Ipsen within 7 calendar days.

Medication error

Medication error is an unintended failure in the drug treatment process that leads to, or has the potential to lead to harm to the participant.

Medication error should be reported as AEs in the AE eCRF whether or not they were associated with a clinical event. All medication error should be reported to Ipsen within 7 calendar days.

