8.4.4 Safety Analysis

Safety analyses will be performed on the Safety population.

During the Treatment Period (Visit 2 to Visit 9), all treatment-emergent AEs including nonserious AEs and SAEs and SS including pregnancy will be collected.

Analysis of AEs

A treatment-emergent AE is defined as any AE that occurs after the first dose of study treatment if:

- It was not present prior to receiving the first dose of study treatment; or
- It was present prior to receiving the first dose of study treatment but the intensity increased during the active phase of the study.

The focus of analysis of this study will be the duration of the Treatment Period, i.e. up to 30 days after the permanent discontinuation of cabozantinib.

An overall summary table of all AEs (including fatal events) will be presented with the number and proportion of participants and the number of events, including frequency of SAEs, drug-related AEs and drug-related SAEs. Summary incidence tables of all AEs, SAEs and AEs by relationship and intensity/grade to study drug will be provided, classified by primary System Organ Class (SOC) and Preferred Term (PT).

All AEs will be coded according to the Medical Dictionary for Regulatory Activities (MedDRA) and will be classified by MedDRA PT and SOC.

All safety data will be included in the participant data listings, such as listings of all AEs, SAEs, AEs leading to study drug withdrawal, AEs leading to dose reduction or interruption and listings of deaths.

Analysis of "Special Situation"

SSs will be listed separately, and summary incidence tables will be provided. The AEs associated with SSs will be described.

PAGE 37/52

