9 MANAGEMENT AND REPORTING OF ADVERSE EVENTS/ADVERSE DRUG REACTIONS AND SPECIAL SITUATIONS

9.1 Definition

9.1.1 Adverse Event

AE Definition

An Adverse Event (AE) is any untoward medical occurrence in a patient/participant, administered a medicinal product (cabozantinib) and which does not necessarily have a causal relationship with this treatment.

NOTE: An AE can therefore be any unfavourable and unintended sign (e.g. an abnormal laboratory finding), symptom, or disease temporally associated with the use of the medicinal product, whether or not related to the medicinal product.

Events Meeting the AE Definition

Any abnormal laboratory test results (haematology, clinical chemistry, or urinalysis) or other safety assessments (e.g. ECG, radiological scans, vital signs measurements), including those that worsen from baseline, considered clinically significant in the medical and scientific judgement of the investigator (i.e. not related to progression of underlying disease).

Exacerbation of a chronic or intermittent pre-existing condition including either an increase in frequency and/or intensity of the condition.

New condition detected or diagnosed after study treatment administration even though it may have been present before the start of the study.

Signs, symptoms, or the clinical sequelae of a suspected drug-drug interaction.

Signs, symptoms, or the clinical sequelae of a suspected overdose of either study treatment or a concomitant medication. Overdose per se will not be reported as an AE/SAE unless it is an intentional overdose taken with possible suicidal/self-harming intent. Such overdoses should be reported regardless of sequelae.

For studies involving marketed products in established indications include:

The signs, symptoms, and/or clinical sequelae resulting from lack of effectiveness will be reported as AE or SAE if they fulfil the definition of an AE or SAE. Also, "lack of effectiveness" or "failure of expected pharmacological action" also constitutes an AE or SAE.

Events NOT Meeting the AE Definition

Any clinically significant abnormal laboratory findings or other abnormal safety assessments which are associated with the underlying disease, unless judged by the investigator to be more severe than expected for the participant's condition.

The disease/disorder being studied or expected progression, signs, or symptoms of the disease/disorder being studied, unless more severe than expected for the participant's condition.

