Medical or surgical procedure (e.g. endoscopy, appendectomy): the condition that leads to the procedure is the AE.

PAGE 39/52

Situations in which an untoward medical occurrence did not occur (social and/or convenience admission to a hospital).

Anticipated day-to-day fluctuations of pre-existing disease(s) or condition(s) present or detected at the start of the study that do not worsen.

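### Section 9.1.3.2 makes every overdose an AE even without a clinical event, contradicting 9.1.1; its parallel wording for off-label use, misuse and medication error sits badly with the AE definition

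*Protocol*

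**What the plan says.** Protocol section 9.1.1 defines an AE as an untoward medical occurrence in a participant given cabozantinib. On overdose it states: "Overdose per se will not be reported as an AE/SAE unless it is an intentional overdose taken with possible suicidal/self-harming intent". Its list of what does not meet the definition includes "Situations in which an untoward medical occurrence did not occur", illustrated by a social or convenience admission.

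Section 9.1.3.2 gives sites a different instruction for overdose: "Overdoses should be reported as AEs in the AE eCRF page whether or not they were associated with a clinical event". It repeats the rule for three further categories that need involve no harm: "Off-label use should be reported as AEs in the AE eCRF page whether or not they were associated with a clinical event", "Misuse should be reported as AEs in the AE eCRF page whether or not they were associated with a clinical event" and "Medication error should be reported as AEs in the AE eCRF whether or not they were associated with a clinical event".

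Elsewhere the protocol treats SS as a stream of their own. Section 9.1.3 has them reported with or without an associated AE. The table in 9.2.2 gives them a separate row with a 7-day clock (pregnancy: 24 hours). Section 8.4.4 says "SSs will be listed separately, and summary incidence tables will be provided", and adds that AEs associated with SS will be described. Section 6.2 names overdoses beside adverse events as a distinct item, and footnote g to Table 4-1 already captures overdoses under the cabozantinib regimen.

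**The concern.** Two instructions in one protocol decide differently whether the same overdose becomes an AE record, and up to 50 centres (section 4.1) will have to choose between them. Differences in overdose entries between sites would then partly reflect which section each site read.

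The other problem is what the AE tables would contain. Frequency, grade and causality of AEs are secondary endpoints in section 3. An AE record made for a departure from the label, or for an error that reached no one, has no clinical content to grade or attribute, yet sections 9.2.1 and 9.3 ask for both. Any grade entered would be arbitrary. If it were left blank, it would drop out of percentages, which section 8.4 bases on non-missing observations.

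**Working it through.** The protocol gives no figure to reproduce on this point, so the check is a comparison of texts. Take each situation occurring **without** any clinical event.

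| Situation, no clinical event | Under 9.1.1 | Under 9.1.3.2 | Conflict |
|---|---|---|---|
| Overdose, no self-harm intent | Not an AE (named) | AE | Explicit |
| Overdose, possible self-harm intent | Reported regardless of sequelae | AE | None |
| Off-label use | Not named; definition not met | AE | Inferred |
| Misuse | Not named; definition not met | AE | Inferred |
| Medication error | Not named; definition not met | AE | Inferred |
| Abuse | Not named | AE | None shown: the definition in 9.1.3.2 includes harmful effects |
| Occupational exposure | Not named | AE, but without the clause covering absence of a clinical event | Not shown |

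The inference for the three middle categories has two supports.

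1. An AE needs an untoward medical occurrence. Section 9.1.3.2 itself defines medication error to include a failure with only the potential for harm, so its own definition covers cases where nothing untoward happened.
2. Reporting an SS whether or not it comes with an AE (9.1.3), and describing the AEs associated with SS (8.4.4), make sense only if an SS is not automatically an AE.

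Following one event-free record through the plan as written:

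- 9.1.3.2 puts it on the AE page.
- 9.2.1 has it assessed for grade, causality, outcome, action taken and seriousness; 9.3 specifies CTCAE version 5.0.
- 8.4.4 counts it in the incidence tables of all AEs by SOC and PT, relationship and grade, with no stated exclusion.
- 8.4.3.3 (DCR and ORR by number and grade of related AEs) is reached only if the investigator judges the entry related.

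Size, by assumption only: if k participants had such a record and all 150 planned participants were in the safety population, the tables would show k/150 with no underlying event.

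- k = 1: 1/150 = 0.7%
- k = 10: 10/150 = 6.7%

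Nothing in the protocol says which k is realistic. The proportion of participants with any AE would rise by less than k/150 wherever some of the k already have a genuine AE.

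**The case against.** The strongest reply is that only overdose is contradicted in terms. Section 9.1.1 does not name off-label use, misuse or medication error, and its exclusion of situations without an untoward occurrence is illustrated by hospital admissions, not drug-use errors. Section 9.1.1 also counts lack of effectiveness as an AE, while 9.1.3 lists it as an SS, so the protocol does not keep the two streams wholly apart. This stands as a limit: outside overdose the conflict is inferred.

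A second reply is that 9.1.3.2 governs data capture, and that screening SS-only rows out of AE tables is detail that section 8 leaves to the SAP. That is fair for the tables, and a SAP not shown here may do it. It does not answer the capture problem, because a SAP cannot settle what sites enter while two instructions disagree.

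A reader might infer more than the text supports:

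- That all six categories in 9.1.3.2 produce non-events. Abuse is defined there as accompanied by harmful effects, and the occupational-exposure sentence lacks the relevant clause.
- That records are double counted. Appearing in an AE table and in a separate SS table is not double counting, since no planned analysis adds the two.
- That the exploratory response analyses are generally distorted. They use related AEs, and 9.3 asks for facts, evidence or arguments for a causal link, which is hard to meet with no clinical event.
- That the inflation is large. No rates are given, and inclusion requires a treatment decision in line with the SmPC, which should limit off-label use at least at the start.

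**Conclusion.** The point holds in a bounded form. For overdose without self-harm intent and without a clinical event, 9.1.1 and 9.1.3.2 contradict each other outright and must be reconciled. For off-label use, misuse and medication error, the instruction in 9.1.3.2 conflicts by inference with the AE definition and with the handling of SS in 8.4.4, 9.1.3 and 9.2.2.

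The consequence is uneven capture of overdoses across sites and a route for event-free records into the AE incidence, grade and causality tables. That second effect assumes sites follow 9.1.3.2 and that no later exclusion is applied. Its size cannot be stated from the protocol. The primary endpoint is untouched. The point is worth correcting because a safety endpoint is affected and the remedy is cheap.

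**What to change.** Reconcile 9.1.1 and 9.1.3.2 so that an overdose, off-label use, misuse or medication error without a clinical event is recorded as a special situation only. Two routes would work:

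- the SS section of the eCRF, extended if needed, since the protocol expressly assigns it only to pregnancy and breastfeeding; or
- the AE page with a flag marking the record as SS-only.

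In either case, any associated untoward event is recorded as an AE and linked to the SS record. The exception in 9.1.1 for intentional overdose with possible self-harm intent should be repeated in 9.1.3.2 so that the two sections read alike.

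In 8.4.4, add that AE incidence, grade and causality tables exclude SS-only records, which appear in the SS listing and tables.

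Pharmacovigilance loses nothing: 9.1.3 and 9.2.2 already require SS to be reported with or without an AE, and the 7-day clock is unchanged. The cost is protocol and eCRF wording, and possibly some added SS fields or one flag.

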9.1.4 Adverse Events of Special Interest

Not applicable

9.2 Time Period and Frequency for Collecting and Reporting AE, SS and SAE Information

For the definition of the AEs and SS, please refer to Section 9.1.

During the Treatment Period, (i.e. from Day 1 until 30 days after discontinuation of cabozantinib treatment or EoS), all AEs including nonserious AEs and SAEs, and SS will be collected. During the Post-treatment Follow-up Period (i.e. from 30 days after discontinuation of cabozantinib treatment until the EoS), only new AEs assessed as related to cabozantinib that start during this period will be collected. Incidence of pregnancy will be collected until 5 months after EoS. If possible, pregnancy should be followed up until the outcome is known. Any further follow-up information on ongoing AEs (until resolution or stabilisation) and SS including pregnancy that occurred during the Treatment Period will be collected.

PAGE 42/52

From this point onwards, the term 'Safety Report' will collectively refer to all reports of non-serious related AEs, SAEs, fatal outcomes and SS.

9.2.1 Collection of the AEs/SAEs/SS in the eCRF

The collection and reporting of AEs will follow regulations related to non-interventional studies.

All AEs, whether they are serious/nonserious, related/unrelated, and all SS should be collected in the eCRF during the course of the study. Adverse events will be assessed according to incidence, intensity/grade, causality, outcome, action taken and seriousness.

All AEs will be collected in the eCRF from the first intake of cabozantinib until study completion, i.e. EoS or the EoS/follow-up visit, as specified in Table 4-1.

9.2.2 Reporting of SAEs, nonserious ADRs and SS to Sponsor Pharmacovigilance

In order to adhere to all applicable laws and regulations for reporting of a Safety Report, the investigator must report to Ipsen Pharmacovigilance all the following events using the eCRF:

- All serious adverse events (SAEs) related and non-related;
- All related nonserious AEs (ADRs));
- Any SS (see definitions in Section 9.1).

Primary Data Collection NIS		
Safety Event	Collected on the eCRF (observation period)	Reported to Ipsen Global Phar- macovigilance
Non serious adverse event (AE)	All AEs related or not	Only the Related AEs - within 7 calendar days of awareness
Serious adverse event (SAE)	All SAEs related or not	All - within 24 hours of awareness
Pregnancy (as an SS)	All pregnancies	All - within 24 hours of awareness
Special Situations (SS)	All SS related or not (regardless of	All (regardless of whether associ-
	whether associated with an AE)	ated with an AE) - within 7 calen-
		dar days of awareness

All SAEs will be recorded and reported to the sponsor or designee immediately and under no circumstance should this exceed 24 hours (once known), as indicated below. The investigator will submit any updated SAE data to the sponsor within 24 hours of it being available.

All nonserious related AEs and SS will be recorded and reported to the sponsor or designee immediately and under no circumstance should this exceed 7 calendar days (once known), as indicated below.

SAE Reporting to Ipsen Pharmacovigilance via an Electronic Data Collection Tool

• The primary mechanism for reporting an SAE to Ipsen Pharmacovigilance will be the electronic data collection tool.

PAGE 43/52

- If the electronic system is unavailable, then the site will use the paper SAE form "Adverse Event and Special Situation Reporting Form for non-interventional Studies" (134232-FOR) (see next section) in order to report the event within 24 hours.
- The site will enter the SAE data into the electronic system as soon as it becomes available.
- After the study is completed at a given site, the electronic data collection tool will be taken off-line to prevent the entry of new data or changes to existing data.
- If a site receives a report of a new SAE from a study participant or receives updated data on a previously reported SAE after the electronic data collection tool has been taken off-line, then the site can report this information on a paper SAE form (see next section) or to Ipsen Pharmacovigilance department by telephone.
- Contacts for SAE reporting:
 E-mail: PPD
 PPD
 Telephone: PPD

All adverse events will be processed by Ipsen according to their relevant Standard Operating Procedures (SOPs). This includes the follow up of adverse event reports with the investigator, as required.

If an AE occurs with a "non Ipsen product", the investigator should consider informing the competent authority (CA) in the Member State where the event occurred or to the marketing authorisation holder of the suspected medicinal product, but not to both (to avoid duplicate reporting).

Mandatory Information for Reporting an Adverse Event

The following information is the minimum that must be provided to Ipsen's Pharmacovigilance contact within 24 hours for a SAE and within 7 days for a nonserious related AE of awareness for each adverse event:

- Participant identifier
- Product name
- Adverse Event description including assessment of causal relationship and seriousness (See Section 9.3)
- Investigator name and contact details

The additional information included in the adverse event report form must be provided to Ipsen as soon as it is available.

The investigator should report a diagnosis or a syndrome rather than individual signs or symptoms. The investigator should also try to separate a primary adverse event considered as the foremost untoward medical occurrence from secondary adverse events which occurred as complications. The investigator should also provide the batch number and expiry date of the concerned product wherever possible.

PAGE 44/52

9.3 Method of Detecting AEs and SAEs

The method of recording, evaluating and assessing causality of AEs and SAEs and the procedures for completing and transmitting SAE/related AE reports are provided below.

Care will be taken not to introduce bias when detecting AEs and/or SAEs. Open-ended and non-leading verbal questioning of the participant is the preferred method to inquire about AE occurrences.

AE and SAE Recording

- When an AE/SAE occurs, it is the responsibility of the investigator to review all documentation (e.g. hospital progress notes, laboratory reports, and diagnostics reports) related to the event.
- The investigator will then record all relevant AE/SAE information in the eCRF.
- It is not acceptable for the investigator to send photocopies of the participant's medical records to Ipsen Pharma GmbH in lieu of completion of the Ipsen Pharma GmbH AE/SAE CRF page.
- There may be instances when copies of medical records for certain cases are requested by Ipsen Pharma GmbH. In this case, all participant identifiers, with the exception of the participant number, will be redacted on the copies of the medical records before submission to Ipsen Pharma GmbH.
- The investigator will attempt to establish a diagnosis of the event based on signs, symptoms and/or other clinical information. Whenever possible, the diagnosis (not the individual signs/symptoms) will be documented as the AE/SAE.

Assessment of Grade

The investigator will make an assessment of intensity for each AE and SAE reported during the study using the current version of the Common Terminology Criteria for Adverse Events (CTCAE) grading system Version 5.0 (2017).

Assessment of Causality

- The investigator is obligated to assess the relationship between study treatment and each occurrence of each AE/SAE.
- A "reasonable possibility" of a relationship conveys that there are facts, evidence, and/or arguments to suggest a causal relationship, rather than a relationship cannot be ruled out.
- The investigator will use clinical judgement to determine the relationship.
- Alternative causes, such as underlying disease(s), concomitant therapy, and other risk factors, as well as the temporal relationship of the event to study treatment administration will be considered and investigated.
- The investigator will also consult the Investigator's Brochure and/or Product Information, for marketed products, in his/her assessment.
- For each AE/SAE, the investigator must document in the medical notes that he/she has reviewed the AE/SAE and has provided an assessment of causality.
- There may be situations in which an SAE has occurred and the investigator has minimal information to include in the initial report to Ipsen Pharma GmbH. However, it is

PAGE 45/52

- very important that the investigator always make an assessment of causality for every event before the initial transmission of the SAE data to Ipsen Pharma GmbH.
- The investigator may change his/her opinion of causality in light of follow-up information and send a SAE follow-up report with the updated causality assessment.
- The causality assessment is one of the criteria used when determining regulatory reporting requirements.

